# 3.3. Benefit/Risk Assessment

IFX-1 is a drug that has been safely administered to more than 300 subjects. In non-clinical safety studies, a NOAEL of mg/kg has been established resulting in pharmacokinetic NOAEL PK values, which will not be reached in this study based on the simulations stated in section 3.2.5.1 of this protocol. unexplained death occurred in cynomolgus monkey during the non-clinical safety studies, which retrospectively showed development of anti-IFX-1 antibodies, and resulting circulating immune complexes, which has been described in monkeys before. In humans, this chimeric IgG4 antibody has the potential to elicit infusion-related reactions, including

hypersensitivity or anaphylaxis. However, there have only been few cases of anti-IFX-1 antibody formation, and only mild to moderate signs of hypersensitivity reactions were observed so far in study patients (overall ADA rate in the range of \(\bigcirc\)\(\text{\omega}\)\(\text{\omega}\)\). In total, IFX-1 showed very good tolerability in clinical studies. The majority of observed AEs were attributed to the underlying diseases and IFX-1 AESIs occurred occasionally (see IFX-1 \(\text{IB}\) for details).

Preclinically, C5a has been shown to support tumor development and metastasis and to contribute to an immunosuppressive TME, in particular in SCC. In addition, the combination of anti-C5a and anti-PD1 directed therapy led to tumor regressions in anti-PD1 therapy resistant melanoma mouse models.

IFX-1 leads to an almost complete blockade of C5a-induced biological effects and prevents C5a-mediated inflammatory signaling. In vitro and in vivo, C5a blockade does not interfere with activation of the classical component cascade, generation of other anaphylatoxins C3a and C4a, and assembling of the membrane attack complex.

The potential risks associated with the intravenous administration of IFX-1 due to its mode of action include the following:

*Infections:* Potent inflammatory response mechanisms, such as neutrophil oxygen radical species generation, are decreased upon C5a blockade. Infections are therefore identified as an anticipated important potential risk associated with IFX-1 treatment (Section 7.6.4 of the IFX-1 IB). Therefore, investigators (and other health care professionals) should be vigilant for signs and symptoms of infections in general.

Meningitis/meningococcal sepsis: To date, no cases of meningitis or meningococcal sepsis have been reported in clinical studies with IFX-1 (Section 7.6.3 of the IFX-1 IB). Therefore, mandatory vaccination or concomitant broad-spectrum antibiotic treatment is not warranted based on the mode of action for IFX-1. However, until more patients have been exposed to IFX-1, specific attention should be given to any signs of meningitis in this context and immediate appropriate measures should be taken as described in Section 7.6.3 of the IFX-1 IB.

Infusion-related reactions/hypersensitivity reactions: Because IFX-1 is an antibody/protein, a general risk for infusion-related reactions, including hypersensitivity or anaphylaxis, exists (Section 7.6.2 of the IFX-1 IB). Participating study sites are required to be able to provide adequate treatment and care in case of an anaphylactic reaction. To date, no anaphylactic reactions have been reported after administration of IFX-1 in completed clinical Phase I and Phase II studies.

So far, the PD-1 checkpoint inhibitors cemiplimab and pembrolizumab are the only approved therapies for locally advanced or metastatic cSCC. For patients with locally advanced or metastatic

cSCC, who have not responded or have progressed on cemiplimab, pembrolizumab, or another PD-1/PD-L1-directed therapy, no other efficacious therapy exists currently.

Because no efficacious therapy is currently available in the setting of PD-1 or PD-L1-refractory or resistant locally advanced or metastatic cSCC and a good AE profile was observed for IFX-1 so far, the hypothesized benefit outweighs the potential risks for the patients participating in this study.

More detailed information about IFX-1, the known and expected benefits and risks, including safety experience gained in clinical studies investigating inflammatory diseases, may be found in the IB.

# 4. OBJECTIVES AND ENDPOINTS

# 4.1. Study Objectives

# 4.1.1. Monotherapy Arm A

### Primary objective:

• To assess the antitumor activity of IFX-1

# Secondary objectives:

- To further assess efficacy of IFX-1
- To assess the safety profile of IFX-1
- To assess the PK of IFX-1
- To monitor the immunogenicity of IFX-1
- To assess the impact of IFX-1 on quality of life (QoL)

# Other objectives:

- To describe the TME in primary tumor samples and metastases
- To assess pharmacodynamic effects of IFX-1 in skin tumors and peripheral blood
- To describe oncogenic alterations of the tumor at baseline

# 4.1.2. Combination Therapy Arm B

# Primary objectives:

# Safety run-in part

• To determine the maximum tolerated dose (MTD) or recommended Phase II dose (RP2D)

# Phase II portion

- To assess the antitumor activity of IFX-1 + pembrolizumab
- To assess the safety profile of IFX-1 + pembrolizumab

# Secondary objectives:

- To further assess efficacy of IFX-1
- To assess the PK of IFX-1
- To monitor the immunogenicity of IFX-1
- To assess the impact of IFX-1 + pembrolizumab on QoL

# Other objectives:

- To describe the TME in primary tumor samples and metastases
- To assess the pharmacodynamic effects of IFX-1 + pembrolizumab in skin tumors and peripheral blood
- To describe oncogenic alterations of the tumor at baseline

# 4.2. Study Endpoints

# 4.2.1. Primary Endpoints

#### 4.2.1.1. Monotherapy Arm A

The primary endpoint of monotherapy Arm A is investigator assessed best overall response rate (ORR) for IFX-1, with response being defined as best response of complete response (CR)/confirmed CR (iCR) or partial response (PR)/confirmed PR (iPR) per modified response evaluation criteria in solid tumors (RECIST) version 1.1/RECIST for immune-related therapeutics (iRECIST).

# **4.2.1.2.** Combination Therapy Arm B

Safety run-in part

The primary endpoint of the safety run-in part of combination therapy Arm B is the frequency of dose-limiting toxicities (DLTs) by dose cohort.

# Phase II portion

The co-primary endpoints of the Phase II portion of Arm B are investigator assessed best ORR for IFX-1 + pembrolizumab, with response being defined as best response of CR/confirmed CR (iCR) or PR/confirmed PR (iPR) per modified RECIST v1.1/iRECIST and frequency, severity, and investigational new drug (IND) attribution of TEAE and serious adverse event (SAE) according

to the Medical Dictionary for Regulatory Activities (MedDRA) coding (version valid at time of reporting) and the NCI CTCAE grading system v5.0.

# 4.2.2. Secondary Endpoints

# 4.2.2.1. Monotherapy Arm A

Secondary endpoints comprise the following:

- Response (CR/iCR/PR/iPR) and stable disease (SD) duration
- Disease control rate (CR/iCR+PR/iPR+SD)
- PFS
- OS
- Frequency, severity, and IND attribution of treatment-emergent AEs (TEAEs) and SAEs according to MedDRA coding (version valid at time of reporting) and the National Cancer Institute common terminology criteria for AEs (NCI CTCAE) grading system (version 5.0, 27 November 2017)
- Post infusion ( $C_{max}$ ) and trough concentration ( $C_{trough}$ ) of IFX-1
- Development of human ADAs against IFX-1
- Changes in QoL as per the European Organisation for Research and Treatment of Cancer (EORTC)-QoL questionnaire (QLQ)-C30 total score

# 4.2.2.2. Combination Therapy Arm B

Secondary endpoints comprise the following:

- Response (CR/iCR/PR/iPR) and SD duration
- Disease control rate (CR/iCR+PR/iPR+SD)
- PFS
- OS
- Cmax, and Ctrough of IFX-1
- Development of human ADAs against IFX-1
- Changes in QoL as per the EORTC-QLQ-C30 total score

# **4.2.3.** Explorative Endpoints

Other endpoints across both arms are:

- Tissue-based biomarkers in skin-based tumor lesions, before and during IFX-1 administration
- C5a concentration in plasma before treatment start, during treatment, and at treatment discontinuation

# 5. STUDY DESIGN

# 5.1. Overall Design

The study is an open-label, non-randomized, 2-stage, 2-arm, Phase II study, investigating antitumor activity of IFX-1 alone or IFX-1 in combination with pembrolizumab for the treatment of locally advanced or metastatic PD-1- or PD-L1-resistant/refractory cSCC.

It is planned to include up to approximately 70 patients in the 2 arms: IFX-1 monotherapy Arm A and IFX-1 + pembrolizumab combination therapy Arm B.

Arm A consists of 2 stages where patients will receive IFX-1 monotherapy (see Section 5.2.1).

[figure not shown]
Arm B will start after ≥3 patients have been treated in Arm A and no toxicity concerns have emerged. Arm B consists of a safety run-in part in Stage 1 with 3 dose cohorts, and a Phase II portion in Stage 1 and Stage 2 (see Section 5.2.2 and Figure 1). In the 3 dose cohorts of the safety run-in, escalating doses of IFX-1 will be investigated in combination with 400 mg pembrolizumab every 6 weeks [Q6W], in order to identify the MTD. 6 patients will need to be treated at the MTD or at the highest IFX-1 dose level (Regimen 3, if MTD was not reached) to decide if this dose can be selected as RP2D which will then be explored in the Phase II portion of Arm B. In case only 3 patients will have been previously treated at the MTD or highest IFX-1 dose level, 3 more patients will be added to this cohort. If 6 patients were already treated at the proposed dose level, then additional patients will not be required and the decision on the RP2D will be made based on the available data.

Patients will be treated until disease progression, occurrence of unacceptable toxicity, or treatment discontinuation for any other reason.

Patient enrollment into each of the treatment arms follows an optimal Simon's 2-stage design (Simon, 1989) with an interim analysis of treatment response after Stage 1 prior to patient enrollment into Stage 2 (see Section 10.3.4).

Patients will be assigned to treatment Arm A or B as enrollment rules allow and stratified by locally advanced or metastatic cSCC.

# A schematic overview of the overall study design and patient enrollment is given in Figure 1 Figure 1 Study Design

CR: complete response; DLT: dose-limiting toxicity; LA: locally advanced; mcSCC: metastatic cutaneous squamous cell carcinoma; N: number of patients; PD1: programmed cell death 1 protein; PD-L1: programmed cell death ligand 1; PR: partial response.

The IFX-1 dosing in Stage 2 of Arm B will be IFX-1 dose in regimens 1, 2, or 3 depending on the maximum tolerated dose (MTD) or recommended Phase II dose (RP2D) from Stage 1. In case only 3 patients have been previously treated at the MTD or highest IFX-1 dose level, then 3 more patients will be enrolled into the respective dose level cohort before the dose can be finally selected for Stage 2.

.

A steering committee will be established to support the patient enrollment in both treatment arms and monitor patient safety throughout the study. For further details see Section 5.3.

# **5.1.1.** Method of Treatment Assignment

Patients will be centrally assigned to a treatment arm by the Sponsor according to proceeding of enrollment and safety evaluation by the steering committee (see Section 5.3). Treatment assignment will be stratified by locally advanced or metastatic cSCC; ≥3 out of 10 in Stage 1 and ≥9 out of 29 patients in Stage 2 in each treatment arm must have either locally advanced or metastatic disease at time of (interim) analyses. The investigational medicinal product (IMP) will be centrally assigned using an Interactive Web Response System (IWRS). Before the study is initiated, user access codes (log in information), user instructions, and training will be provided to responsible personnel at each site.

IMP will be dispensed at the study visits as summarized in the schedule of assessments (SoA, Table 1).

Returned IMP must not be re-dispensed to the patients.

# 5.1.2. Blinding

This is an open-label study; however, the IMP kit numbers will be assigned to each patient using an IWRS. The site will contact the IWRS prior to the start of IMP for each patient. The site will record the IMP assignment on the applicable case report form if required.

# **5.2.** Patient Enrollment

A Simon's 2-stage design will be applied in each independent cohort/treatment arm.

After informed consent, screening procedures are to be performed within 4 weeks before first study treatment administration. For details on the role of the steering committee, see Section 5.3.

# 5.2.1. Monotherapy Arm A

Three patients will be enrolled in treatment Arm A to receive IFX-1 monotherapy. After these three patients have been treated and their safety closely monitored by the steering committee, as described in Section 5.3, enrollment into Arm A will continue with additional 7 patients. If one or more of the 10 patients enrolled in Stage 1 of Arm A have a response evaluation of PR or CR at their third tumor assessment (no confirmation of response evaluation necessary), enrollment of 19 additional patients in Stage 2 of Arm A will continue without specific enrollment rules. If there are no responders in Stage 1 of Arm A, enrollment will be stopped and there will be no Stage 2 for Arm A.

For the definitions of CR and PR refer to Appendix 3.

# 5.2.2. Combination Therapy Arm B

# **5.2.2.1. Safety Run-In**

After  $\geq 3$  patients have been treated in Arm A under close monitoring by the steering committee, the safety run-in of Stage 1 of treatment Arm B will be opened. Patients will be sequentially enrolled into 3 escalating dose cohorts and their safety will be monitored by the steering committee, as described in Section 5.3.2.

The safety run-in part will follow a 3+3 design as described in 10.3.4.2 and monitored by the steering committee: 3 patients will be enrolled in the lowest dose cohort (IFX-1 regimen 1 + pembrolizumab). If 1 of the 3 patients experiences a DLT (see Section 7.2.2.2.3), the cohort will be expanded to a total of 6 patients. If  $\geq 1$  patient of 3 or > 1 patient of 6 develop a DLT, further dose escalation is not pursued, and the next lower dose will be chosen as the MTD (see Section 7.2.2.2.4). If there is no DLT observed in any of the first 3 patients, or in only 1 of 6 patients, 3 new patients will be enrolled in the next higher dose cohort (IFX-1 regimen 2 + pembrolizumab). For the second and third dose cohort (IFX-1 regimen 3 + pembrolizumab), the same rules apply. If the MTD is not reached, the highest dose (IFX-1 regimen 3 + pembrolizumab) will be chosen as potential RP2D (see Section 7.2.2.2.4). 6 patients will have to be treated at the highest IFX-1 or MTD dose level to confirm the respective dose to be used in Stage 2. In case only 3 patients will have been previously treated at the MTD or highest IFX-1 dose level, 3 more patients will be added to this cohort. If 6 patients were already treated at the proposed dose level, then additional patients will not be required and the decision on the RP2D will be made based on the available data. When the MTD or RP2D has been established, Stage 1 of Arm B will continue with the Phase II portion (see Section 5.2.2.2).

#### **5.2.2.2. Arm B Phase II Portion**

After the MTD or RP2D dose have been identified and confirmed, the safety run-in part is completed and, under close monitoring of the steering committee (see Section 5.3), additional patients will be enrolled in Stage 1 of Arm B until 10 patients will have received the RP2D. If  $\geq$ 1 of the 10 patients has a response evaluation of PR/iPR or CR/iCR after their third tumor assessment (confirmation not necessary), enrollment of 19 additional patients in Stage 2 of Arm B will continue without specific enrollment rules. If there are no responders in Stage 1 of Arm B, enrollment will be stopped and there will be no Stage 2 for Arm B.

For the definitions of CR/iCR and PR/iPR refer to Appendix 3 and Appendix 4.

# **5.3.** Steering Committee

A steering committee will be constituted to support the patient enrollment in both treatment arms and monitor patient safety throughout the study. The steering committee will include the clinical study monitor and  $\geq 3$  cSCC experts (principal investigators included). At all safety reviews performed by the Steering Committee, and when reviewing the overall data prior to progression to

stage 2 of the protocol in each treatment arm, the committee will review the adverse event data in the same way as outlined for the definition of DLTs in Section 7.2.2.2.3. Detailed information will be provided in the Steering Committee Charter.

# 5.3.1. Monotherapy Arm A

In Arm A, IFX-1 will be dosed as monotherapy utilizing a dosing regimen that is consistent with prior exposures in the HS patient population (study IFX-1-P2.3) and the pyoderma gangrenosum patient population (study IFX-1-P2.7). In Arm A, the Committee will review the safety after three patients have reached day 36 of their treatment. At this point of time, during their treatment they will have received the fractionated loading dose of 800 mg IFX-1 on days 1, 4, 8, 15 and the first two doses of 1600 mg IFX-1, which means that they will have experienced peak concentrations of IFX-1.

Criteria for the decision to proceed with enrolment in Arm A and to initiate enrollment in Arm B, will be based on assessment of general safety of IFX-1 treatment administration and with specific focus on occurrence of any of the following conditions:

If any of these conditions occur in the first 3 patients treated with IFX-1 monotherapy, the steering committee will assess safety data and give recommendation on whether more patients should be enrolled into monotherapy Arm A before recruitment in Arm B may commence.

The steering committee will continue assessing the totality of safety information during the meetings scheduled for the review of the safety of the Combination Therapy Arm B.

# 5.3.2. Combination Therapy Arm B

In Arm B, during the safety run-in for each combination regimen cohort, the first 2 patients must be enrolled sequentially separated by a minimum of one week.

At the following time points, the Committee will review patient safety:

- For the very first patient receiving the combination therapy: After Cycle 1, Day 36, when this patient will have received the four consecutive IFX-1 fractionated loading dose administrations, one pembrolizumab administration, and two of the higher IFX-1 Q2W doses (to allow inclusion of subsequent patients)
- For each escalating dosing regimen: After 3 patients of each combination regimen cohort will have reached Cycle 1, day 36, at which they will have received the four consecutive IFX-1 fractionated loading dose administrations, one pembrolizumab administration, and two of the higher IFX-1 Q2W doses (to determine occurrence of DLT and necessity to include 3 more patients in a given dose cohort, to allow treatment in the next higher dose cohort, or to determine the MTD or RP2D)

To determine the RP2D, 6 patients should be treated at the MTD or highest dose level. If only 3 patients will have been enrolled into the respective cohort, 3 more patients will be enrolled at the same dose level. If no further toxicities are observed, this MTD will be selected as dose for Stage 2 and recommended combination regimen. Further patient enrollment in Arm B can proceed without specific rules.

The steering committee will continue to meet every three months until the last patient will have completed the third month of treatment in Stage 1 of the study and every six months thereafter to further confirm safety of the MTD or RP2D, and to further assess general safety of study treatment administration. All available safety data will be provided to the steering committee before each meeting.

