#### 7.2.2.2.4. Maximum Tolerated Dose

The MTD is defined as the highest dose at which  $\leq 1$  of 3 patients or  $\leq 1$  of 6 patients (in an expanded cohort) experience a DLT with IFX-1 in combination with 400 mg pembrolizumab. Thus, the MTD is defined as the dose level immediately below the level at which dosing is stopped due to the occurrence of >1 DLT in a cohort with 3 patients or of >1 DLT in an expanded cohort of 6 patients. If dose escalation is not stopped due to the occurrence of DLTs, it will be considered that the MTD has not been determined and the highest IFX-1 dose level will be considered as dose for Stage 2. 6 patients will need to be treated at the MTD or at the highest IFX-1 dose level (Regimen 3, if MTD was not reached) to decide if this dose can be selected as RP2D which will then be explored in the Phase II portion of Arm B. In case only 3 patients will have been previously treated at the MTD or highest IFX-1 dose level, 3 more patients will be added to this cohort. If 6 patients were already treated at the proposed dose level, then additional patients will not be required and the decision on the RP2D will be made based on the available data.

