## 10.3.4.2. Safety Run-In Based on 3+3 Design (Combination Therapy Arm B)

The safety run-in phase in the combination Arm B will follow a 3+3 design for escalation of the IFX-1 treatment regimen based on the following escalation rules:

• If 0 of 3 patients experience a DLT during the DLT observation period (see Section 7.2.2.2.3) at a certain IFX-1 treatment regimen, the subsequent 3 patients will be enrolled in the next higher IFX-1 treatment regimen.

- If 1 of 3 patients experience a DLT, another 3 patients will be enrolled at the same IFX-1 treatment regimen.
  - If 1 of 6 patients (i.e., none of the subsequent 3 patients) experiences a DLT, the combination arm will escalate to the next IFX-1 treatment regimen.
  - If ≥1 of 6 patients at the same IFX-1 treatment regimen experience a DLT, this treatment regimen will be stopped.
- If >1 of 3 patients at the same IFX-1 treatment regimen experience a DLT, this treatment regimen will be stopped.
- If a treatment regimen is stopped, the next lower treatment regimen is considered as MTD.
- In the highest IFX-1 treatment regimen (regimen 3): if ≤1 of 6 patients experience a DLT, this will be determined as RP2D.
- 6 patients will need to be treated at the MTD or at the highest IFX-1 dose level (Regimen 3, if MTD was not reached) to decide if this dose can be selected as RP2D which will then be explored in the Phase II portion of Arm B. In case only 3 patients will have been previously treated at the MTD or highest IFX-1 dose level, 3 more patients will be added to this cohort. If 6 patients were already treated at the proposed dose level, then additional patients will not be required and the decision on the RP2D will be made based on the available data.
- The subsequent patients will be enrolled at the RP2D to fill up the first stage of the Simon's 2-stage design for the combination arm (4 additional patients to reach the required sample size of 10).

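### Section 5.3.2 confirms the Arm B Stage 2 dose on no further toxicities in the added patients, while Sections 7.2.2.2.4 and 10.3.4.2 accept 1 DLT in 6, and Section 10.3.4.2 also contradicts itself on that count

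*Combined protocol and SAP*

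**What the plan says.** Arm B needs six patients at the MTD, or at the highest IFX-1 regimen if no MTD is reached, before a dose goes forward. Section 5.3.2 says: "If only 3 patients will have been enrolled into the respective cohort, 3 more patients will be enrolled at the same dose level". Its next sentence is the confirmation rule: "If no further toxicities are observed, this MTD will be selected as dose for Stage 2 and recommended combination regimen". That sentence gives no grade, no relatedness criterion, no permitted count, and no consequence if a toxicity is seen.

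Other sections set limits for the same six patients:

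- **Section 5.3** says that at all safety reviews "the committee will review the adverse event data in the same way as outlined for the definition of DLTs in Section 7.2.2.2.3".
- **Section 7.2.2.2.4** defines the MTD as the highest dose at which at most 1 of 3, or at most 1 of 6, "patients (in an expanded cohort) experience a DLT with IFX-1 in combination with 400 mg pembrolizumab". It describes dosing as stopped "due to the occurrence of >1 DLT in a cohort with 3 patients or of >1 DLT in an expanded cohort of 6 patients". It sets no separate numeric cut-off for the RP2D. If six patients have already been treated, "the decision on the RP2D will be made based on the available data".
- **Section 10.3.4.2** states: "In the highest IFX-1 treatment regimen (regimen 3): if ≤1 of 6 patients experience a DLT, this will be determined as RP2D". The same list escalates when 1 of 6 patients has a DLT, and it also stops a regimen when 1 or more of 6 have one.
- **Section 5.2.2.1** says the run-in follows the 3+3 design of Section 10.3.4.2 under steering committee monitoring. It escalates after 1 DLT in 6 and ends escalation at more than 1 in 6. It both expands a cohort after 1 DLT in 3 and ends escalation at 1 or more in 3.

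**The concern.** The confirmation step fixes the IFX-1 dose for the Phase II portion of Arm B. It therefore determines which run-in patients count towards the 10 of Stage 1 and the 29 of the final analysis. If the sections disagree on what the six patients must show, the same data can support opposite decisions. The choice between them would then be made after the results are known, in an open-label trial.

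The step lies on an ordinary path through the plan. If no DLT occurs in the first 3 patients of any regimen, the run-in uses 3 + 3 + 3 patients and then adds 3 at regimen 3. That gives 12, the minimum run-in size stated in Section 5.4.

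**Working it through.** The documents give no operating characteristics for the run-in, so there is no stated figure to reproduce. The check has two parts.

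**1. The rules side by side, reading toxicities as DLTs**

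| DLTs at the final dose | MTD definition, 7.2.2.2.4 | RP2D line, 10.3.4.2 (regimen 3) | Stop line, 10.3.4.2 (1 or more of 6) | Condition in 5.3.2 |
|---|---|---|---|---|
| 0/3, then 0/3 | met | met | not triggered | met |
| 0/3, then 1/3 | met | met | triggered | **not met** |
| 0/3, then 2/3 or 3/3 | not met | not met | triggered | not met |
| 1/3, then 0/3 (already at 6) | met | met | triggered | does not apply |

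Section 5.3.2 parts from the MTD definition and the RP2D line in the second row. The stop line parts from them in the second and fourth rows. In the fourth row the escalation line for 1 of 6 says to go on while the stop line says to stop, so Section 10.3.4.2 disagrees with itself whatever Section 5.3.2 means.

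**2. How often the second row occurs**

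Inputs: 3 initial and 3 added patients (Section 5.3.2). The per-patient DLT rate p is an assumption, varied from 5% to 30%, because the documents give none. Patients are treated as independent.

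P(0/3, then exactly 1/3) = (1−p)³ × 3p(1−p)²

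- p = 5%: 0.8574 × 0.1354 = 0.116
- p = 10%: 0.729 × 0.243 = 0.177
- p = 20%: 0.512 × 0.384 = 0.197
- p = 30%: 0.343 × 0.441 = 0.151

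The second factor is the chance of the split once a cohort has shown 0/3 and is expanded: 13.5%, 24.3%, 38.4% and 44.1%.

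The probability that a dose passes depends on the rule applied. Write a = (1−p)³ and b = 3p(1−p)².

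| Rule | Formula | 5% | 10% | 20% | 30% |
|---|---|---|---|---|---|
| At most 1 DLT in 6 | a² + 2ab | 96.7% | 88.6% | 65.5% | 42.0% |
| No DLT in the added 3 | a² + ab | 85.1% | 70.9% | 45.9% | 26.9% |
| Stopped at 1 or more in 6 | a² | 73.5% | 53.1% | 26.2% | 11.8% |

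Up to rounding, the first and second rows differ by ab, the split path above.

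**The case against.** **The wording is loose, but the meaning is clear from context.** Section 5.3 ties every committee review to the DLT definition. Section 5.3.2 describes the cohort review as establishing whether DLTs occurred. Section 7.2.2.2.3 leaves the final call on a DLT to consensus of investigator, sponsor and committee. This stands as far as it goes. A reader might otherwise infer that any Grade 1 event in one added patient blocks the dose, so that almost every regimen fails. The documents do not support that inference. It sets Section 5.3 aside and needs high event rates that the documents never state: for 95% of regimens to fail, the per-patient rate r must satisfy 1 − (1−r)³ = 0.95, so r is about 63%. The DLT reading does not remove the conflict, however, because the second row of the first table already assumes it.

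**Section 5.3.2 covers only the clean case.** It says the dose is selected if nothing further is seen. It does not say the dose is rejected otherwise, so the 3+3 rules could fill the gap. This is fair: a strict only-if reading is an inference. But the section then gives no instruction for 1 DLT among the added 3, and the rules that would fill the gap conflict on exactly that count.

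**The committee is pointed to Section 10.3.4.2.** Section 5.2.2.1 does this. A reader might infer that the committee follows one section and the statistician another, but nothing in the documents says so. The cross-reference still leads to a list that both accepts and stops at 1 of 6.

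**The gap is narrow.** It needs a final cohort of 3 with no DLT and then exactly 1 DLT in the added 3. A cohort already at 6 is not expanded again. This stands. The percentages describe one cohort and are not the chance that the trial meets the problem.

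**Conclusion.** Wrong as written. Section 5.3.2 sets a confirmation condition with an undefined event and no stated consequence. Read as DLTs, that condition is not met by a cohort with 0 of 3 and then 1 of 3, although the cohort satisfies the MTD definition in Section 7.2.2.2.4. For regimen 3 it also satisfies the RP2D line in Section 10.3.4.2. Separately, the stop line in Section 10.3.4.2 contradicts that section's own escalation and RP2D lines at 1 of 6.

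The size rests on assumed DLT rates and independent patients: about 12% to 20% per cohort for true rates between 5% and 30%, confined to a final cohort that had 3 patients. If the committee in practice treats 1 in 6 as acceptable, nothing changes in the trial, but the documents do not settle that. Which count is right is for the sponsor to decide.

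**What to change.** Reconcile Sections 5.3.2, 7.2.2.2.4 and 10.3.4.2, together with the matching text in Section 5.2.2.1:

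- State one rule for the six patients at the MTD or highest dose. Use one event type (the DLT of Section 7.2.2.2.3, or another defined term used throughout) and one permitted count. The sponsor chooses the count.
- Say what happens to the dose when the count is exceeded.
- Make clear whether the rule applies to every regimen that may become the RP2D, since the numeric line now covers regimen 3 only.
- Bring the stop line for 6 patients in Section 10.3.4.2 into agreement with that section's escalation and RP2D lines. Citing the section unchanged would carry its contradiction over.
- Have Section 5.3.2 cite the rule and drop its own condition, and align the Steering Committee Charter, which was not available for this review.

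The cost is a few sentences in a protocol amendment and a check of the Charter. Sample size, visits and data collection do not change.
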